1.2. Methadone providers

Methadone providers will conduct the study interventions under the clinical supervision of the study master counselors. All methadone providers have been trained on basic addiction medicine and will receive further training to deliver the study interventions. We will conduct in-depth interviews with them before and after the intervention phase.

Randomization and Interventions

An investigator will stratify participants by HIV status and randomize them into two frontline interventions using REDCap, as shown in Figure 1. She will send the allocation results to the site research assistants who will then inform providers at the study clinics. This is an open label study so unblinding does not occur. Participants and their counselors, research assistants and data managers are aware of participants' assignment of intervention. Participants will receive two individual sessions of motivational interviewing with their counselors before they get into the frontline interventions and, in Week 13, before the adaptive strategies start. These sessions would boost participants' motivation for intervention and provide them with greater details of the upcoming intervention activities.

Two frontline interventions (Weeks 1-12)

- High intensity: Participants in this arm receive contingency management with the escalating-and-reset schedule throughout 12 weeks. This schedule means participants receive increasing rewards for consecutive negative UDS but if the streak of negative UDS is broken,

their rewards return to the starting level. The maximal reward value over 12 weeks is \$150 USD, equivalent to the average monthly income of our participants.

- Low intensity: Participants in this arm receive contingency management for the first six weeks with the maximal reward value of \$40 USD. For the last six weeks, they attend weekly group education sessions. The topics of group education include 1) Addiction mechanism, 2) Road to recovery, 3) Coping with triggers, 4) Boredom, 5) Building trust and 6) Relapse prevention.

Participants with four consecutive UDS negative with methamphetamine in weeks 11 and 12 are considered to be responsive to frontline interventions. Others are considered non-responsive. Responders to frontline interventions are placed in the maintenance treatment arm. Non-responders are randomized to either enhanced treatment 1 or 2.

Three adaptive strategies (Weeks 14-25)

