We will conduct activity-based costing for each intervention arm over the 20 methadone clinics. A template developed by UNAIDS is adapted to collect data on salaries for personnel and consultants, physical resources, clinical supplies and miscellaneous charges necessary to deliver each intervention type. Furthermore, any out-of-pocket or indirect costs to the participant will be collected at baseline, and at 13- and 26-week.

Definition of cost-effectiveness measures

Measures of cost-effectiveness analysis corresponded to the outcomes of interest in Aim 1 including (1) Substance use, (2) HIV risk behaviors among HIV-negative participants and HIV viral load, HIV adherence among HIV-positive participants and (3) Quality of life (Table 1). The cost-effectiveness analysis will measure the increment in cost between contrasted interventions divided by the increment in effectiveness measures.

Ethnographic evaluation

Pre-post intervention in-depth interviews

In each cluster, we will interview 12 key informants including methadone providers, clinic managers and participants under methadone treatment participating in the study. We will select at minimum 6 participants under treatment so that include old and young, employed and unemployed, and both responsive and non-responsive participants. All participants will receive VND 200 000 (~\$10 USD) for their time in each interview. Interviews will be audio-recorded and transcribed verbatim.

Ethnographic observation

This activity is composed of two elements. The first element involves ethnographers spending time with participants with their consent in intervention sessions and other daily activities in the clinic. Such observations will build a rich picture of interventions and intervention settings, including interactions between various groups (intervention providers, other staff, and participants). The second element involves the study master counselors to observe random intervention sessions and assess the fidelity of intervention delivery using a checklist.

Training and fidelity monitoring

In each selected clinic, a physician, two counselors and one nurse will participate in the study as intervention providers. The physician will ensure referral to HIV and psychiatric services when

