Barriers to access to care	X		X	X
BACE				
Mental health	X		X	X
Depression, Anxiety, Stress Scale (DASS-21)				
Social support	X		X	X
(MOS-SS)				
Quality of life	X			X
(EQ-5D-5L)				
Stigmatisation	X			X
Towards people who are under methadone treatment				
(MMT-SMS)				
Toward people who use drugs				
Toward people living with HIV				
Treatment information (from medical charts)	X	X	X	X
Methadone maintenance treatment				
HIV treatment				
Cost data	X		X	X
Opportunity costs				
Other healthcare costs				
Social costs				
Tests				
Quick and confirmatory HIV tests (not for participants with known HIV seropositivity)	X	X	X	X
Viral load test	X	X	X	X
UDS	Twice a week throughout intervention			X
Ethnographic observation	X	X	X	X
Qualitative interviews	X		X	

Data management

Different datasets collected from different sources will be linked through a unique identification code using REDCap (Research Electronic Data Capture) for quantitative data. Data will be uploaded in real-time from the 20 study clinics onto our database. The study data manager will assess transferred data for completeness, query sites regarding any inconsistencies, and code merged data files for analysis.

For qualitative data, field notes written on site are expanded and recorded electronically within 24 hours. After removing all personal identifiable information, the research team will upload password-protected transcripts on a secured database. The transcripts will be uploaded into Atlas.ti software to organize data and facilitate analysis.

Data analysis

To assess effectiveness

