We will use a time-varying mixed-effects model that will be fitted to the participants' common outcome measures over time. The unadjusted model will include indicators of first-stage and second-stage intervention conditions, time of the assessment (baseline, 13-, 26-, and 49-weeks), and intervention indicators-by-time interaction terms. An additional interaction term of the two intervention indicators will be included to account for any interaction effect between the first and the second stage interventions. The adjusted model will include patients' socio-demographic characteristics, drug use history, HIV-serostatus, and location as fixed effects. The mixed-effects models will include a participant-level random effect to account for repeated observations of each participant, as well as a clinic-level random effect to account for the nested nature within the clinics. We will conduct subgroup analyses among HIV-positive and HIV-negative participants. For the HIV-positive subgroup, the specific outcomes of interest include 1) HIV viral load suppression, and 2) adherence to antiretroviral treatment; and specific outcomes for HIV-negative subgroup include 1) frequency of HIV testing and 2) HIV seroconversion. Substance use will be the common outcomes in models including participants of both HIV statuses.

To assess cost-effectiveness

We will calculate Cost Effectiveness Ratios (CER) for each of the intermediate and final outcomes. The CER is in the broadest terms the difference in per capita costs of administering one intervention (C1-C2) relative to a second, divided by the difference in outcomes between the two interventions (O1-O2):

$$CER = \frac{C1 - C2}{O1 - O2}$$

For example, calculating the CER for adding contingency management to Matrix for non-responders would yield a CER equation. In calculating the CER of high vs. low intensity contingency management at the first randomization stage, the entire range of subsequent costs will be included. Costs of delivering the interventions will be derived from clinic records of time and other inputs, as well as incentive payments, thus providing an estimate of CER from the medical system perspective. We will also evaluate CERs from a societal perspective, using a broad definition of costs, including the social costs of incarceration.

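### The cost-effectiveness plan names no baseline adjustment for the societal cost and quality-of-life differences, although participant costs and EQ-5D-5L are both collected at baseline

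*Combined protocol and SAP*

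**What the plan says.** Under Data analysis, To assess cost-effectiveness, the CER is "the difference in per capita costs of administering one intervention (C1-C2) relative to a second, divided by the difference in outcomes between the two interventions". Definition of cost-effectiveness measures says the same in words: the analysis "will measure the increment in cost between contrasted interventions divided by the increment in effectiveness measures". Neither section names an estimator, a covariate or a baseline term. The planned sensitivity analyses only move the effect and the cost by one standard deviation either way.

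Two cost perspectives are planned.
- Medical system: "Costs of delivering the interventions will be derived from clinic records of time and other inputs, as well as incentive payments".
- Societal: "We will also evaluate CERs from a societal perspective, using a broad definition of costs".

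Baseline data exist for part of this. Definition of costs and data collection says "any out-of-pocket or indirect costs to the participant will be collected at baseline, and at 13- and 26-week". Table 1 also marks cost data at baseline. Its quality-of-life row (EQ-5D-5L) has two marks, at Baseline and Week 49. Quality of life is a named cost-effectiveness measure.

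On the design, Randomization and Interventions says: "An investigator will stratify participants by HIV status and randomize them into two frontline interventions using REDCap". No stratification factor is stated for the later randomisation of non-responders.

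**The concern.** A person's quality of life and out-of-pocket or social costs before treatment can be expected to predict the same person's later values to some degree. If the increments are taken without using those baseline values, two things follow. A chance difference between arms at baseline carries partly into the follow-up difference and is read as an effect or a cost of the intervention. The variance that baseline would have explained also stays in the estimate. Both matter more for the second-stage contrast (Matrix with or without contingency management), because it uses fewer participants.

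At stake is the precision of two components of Aim 2: the societal cost numerator and the quality-of-life denominator. The data that would sharpen them are already being collected. The choice is also open at present, and settling it before results are seen removes the option of picking the more favourable version later.

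**Working it through.** **The plan's own power figure.** None is given for the CER. The only one, under Sample size determination, is a detectable difference of 20 points or more in binary outcomes, with 100 per group, 20% attrition (80 completers), 80% power and 5% alpha (taken as two-sided). Using n = [1.960·sqrt(2·p̄·(1−p̄)) + 0.842·sqrt(p1(1−p1) + p2(1−p2))]² / (p1−p2)²:
- 80% v 60% needs 82 per arm; power with 80 is 0.794.
- 90% v 70% needs 62 per arm; power with 80 is 0.893.

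The figure reproduces to rounding. It concerns other outcomes and is not used below.

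**Inputs.**
- Frontline contrast: 600 participants, 20% attrition, so 480, or 240 per arm. Equal allocation is assumed; the protocol shows it only for the HIV-positive group.
- Second-stage contrast: 50% of 600 (the minimum share given under Modification of eligibility criteria) is 300, or 150 per arm; after 20% attrition, 120 per arm. Equal allocation is assumed.
- Correlation rho between the baseline value and the follow-up quantity: not in the documents. Assumed 0.3, 0.5 and 0.7. For societal cost, rho is the correlation of baseline participant costs with total societal cost. The delivery-cost part of that total has no baseline, which may lower it.

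**Formulas, in SD units, for n per arm.**
- Unadjusted SE = sqrt(2/n)
- Baseline-adjusted SE = sqrt(2/n)·sqrt(1−rho²)
- Change-score SE = sqrt(2/n)·sqrt(2(1−rho))
- 95% range of chance baseline imbalance carried into an unadjusted difference = ±1.96·rho·sqrt(2/n)

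**Results.** Unadjusted SE is sqrt(2/240) = 0.091 (frontline) and sqrt(2/120) = 0.129 (second stage).

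| rho | SE reduction | Frontline adjusted SE | Second-stage adjusted SE | Imbalance carried in, frontline | Imbalance carried in, second stage |
|---|---|---|---|---|---|
| 0.3 | 5% | 0.087 | 0.123 | ±0.05 | ±0.08 |
| 0.5 | 13% | 0.079 | 0.112 | ±0.09 | ±0.13 |
| 0.7 | 29% | 0.065 | 0.092 | ±0.13 | ±0.18 |

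An unadjusted analysis would need 240/(1−rho²) = 264, 320 or 471 per arm to match the adjusted frontline analysis. At rho = 0 nothing is lost. If the non-responder share were the pilot's 38%, the second stage would have about 91 completers per arm (600 × 0.38 / 2 × 0.8). At rho 0.5 the SE would then fall from 0.148 to 0.128, the same 13%.

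**Would the Aim 1 model do the same job?** It has intervention indicators, time (including baseline) and their interaction. EQ-5D-5L has only two time points, so with complete data the intervention-by-time term is a difference in change scores. For the frontline contrast its SE is 0.108, 0.091 and 0.071 at rho 0.3, 0.5 and 0.7. It is therefore less precise than the unadjusted difference below rho 0.5. It is also less precise than baseline adjustment at any rho below 1, because 1−rho² = (1−rho)(1+rho) is smaller than 2(1−rho).

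**The case against.** The strongest reply is that the plan never says the differences are raw. The formula is introduced with a qualifier: "The CER is in the broadest terms the difference in per capita costs of administering one intervention (C1-C2) relative to a second". A ratio of increments is written the same way whether or not the increments are adjusted. This stands. A reader might infer that the plan commits to raw differences, but the text supports only that the estimator is not named and no adjustment is planned.

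Second, the cost-effectiveness measures correspond to the Aim 1 outcomes, and the Aim 1 model contains baseline, with HIV status in its adjusted version. This stands only in part. No text says that model supplies the outcome difference, it is not applied to costs, and quality of life is not among the outcomes named in its description. Its covariate list does not include baseline EQ-5D-5L, and its interaction term would act as a change score.

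Third, the scope is limited, and this stands in full. Delivery costs and incentives have no pre-randomisation value, so baseline costs bear only on the societal numerator. Baseline EQ-5D-5L bears only on the quality-of-life CER. A reader might infer that every CER is affected; the documents do not support that.

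Fourth, the size is hypothetical. Rho is assumed, and EQ-5D-5L is measured almost a year apart; at rho 0.3 the gain is only 5%. Chance imbalance is ordinary sampling error already contained in the unadjusted SE, not bias. A reader might also convert the smaller SE into a gain on the plan's 80% power. That power belongs to the binary outcomes, and the plan states no test or power for the CER. Nor do the documents give the means, SDs or correlations needed to say how far the ratio itself would move.

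**Conclusion.** The point holds as a limited, no-cost improvement, not as an error. The cost-effectiveness section leaves the estimator open and plans no use of baseline values that are already collected for participant costs and quality of life. If the differences were left unadjusted they would be unbiased in expectation, but less precise than the data allow and open to chance imbalance.

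The loss is confined to the societal cost difference and the quality-of-life difference. It depends wholly on the assumed correlation: small at 0.3, worthwhile at 0.5 and large at 0.7. The absolute SEs also assume equal allocation, 20% attrition in both contrasts, a 50% transition to second-stage randomisation and independent participants. The percentage reductions do not depend on the sample size.

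**What to change.** Under Data analysis, To assess cost-effectiveness, state that:
- incremental societal cost is estimated by regression on randomised arm, with baseline participant costs and HIV status;
- incremental quality of life is estimated by regression on randomised arm, with the baseline EQ-5D-5L index and HIV status;
- frontline arm is added to both models for the non-responder contrast;
- the CER is formed from these adjusted differences, kept as mean differences on the original scale, with the unadjusted version as a sensitivity analysis;
- a named model supplies the outcome difference for each of the other cost-effectiveness measures.

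This costs a few sentences, with no new data, visits or staff. The one downside is that participants without a baseline value need imputation, which Analysis of non-adherence and missing data already provides.

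A related item to reconcile in the same edit: the costs section places participant costs at baseline, 13 and 26 weeks, while Table 1 places cost data at baseline, Week 26 and Week 49. The two agree on baseline, so the adjustment does not depend on the answer.

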We will conduct sensitivity analyses to estimate the extent to which the CER calculation is affected by differences in assumptions about the size of the differences in intervention effect. In particular, we will determine how sensitive the CER is to assumptions that the difference in treatment effect is one standard deviation below or above the mean estimated effect size. Similarly, we will estimate the sensitivity of conclusions to costs that are one standard deviation below or above the estimated mean.

To identify the factors influencing the adoption and scale up of the model

The qualitative analysis team will read and provide a narrative summary for each transcript. A codebook will be developed based on these summaries. Memo-writing and code-refining will be conducted throughout the analysis. Iterative analyses assess convergence of patient, provider and organizational dimensions on study measures as well as the context of the policy subsystems, cross system interactions, and resource allocation.

Analysis of non-adherence and missing data

We will first describe the extent and patterns of missingness within each variable, check for associations between missing and observed data to determine the mechanism of missingness, which could be missing completely at random, missing at random, or missing not at random. Missing data will then be handled using multiple imputation (68). Appropriate imputation techniques will be chosen for the type of missing data and the statistical tools employed (69). For sensitivity analysis, we will conduct analyses with and without multiple imputations. All participants will be analyzed on an intent-to-treat basis where the study outcomes are examined based on the random intervention assignment and not on the actual intervention received or adherence to the intervention.

Interim analyses

There is no planned interim analysis as the behavioral therapies used in this trial have no known serious adverse events and are consistently more efficacious than control conditions in treatment-seeking participants. The effect sizes of the behavioral therapies in this trial are in the

moderate range. Furthermore, any interim analysis and decision to stop the trial would likely be based on underpowered data and susceptible to error.

Oversight and Monitoring

Scientific advisory committee

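### The Aim 2 cost-effectiveness ratios have no planned 95% interval and no joint treatment of cost and effect, only separate shifts by an undefined standard deviation

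*Combined protocol and SAP*

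**What the plan says.** Under Data analysis, To assess cost-effectiveness, the plan defines the cost-effectiveness ratio (CER) as a difference in per-person cost "divided by the difference in outcomes between the two interventions (O1-O2"). It is to be calculated for every intermediate and final outcome. Delivery costs come from clinic records of time and inputs "as well as incentive payments, thus providing an estimate of CER from the medical system perspective", and the first-stage comparison takes in all later costs.

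Uncertainty is covered in one short paragraph, introduced as sensitivity analyses. The effect is set "one standard deviation below or above the mean estimated effect size". A second sentence covers the "sensitivity of conclusions to costs that are one standard deviation below or above the estimated mean". Neither sentence says which standard deviation is meant, and no joint variation is described.

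The combined document contains no bootstrap, Fieller interval, net-benefit analysis, probabilistic analysis or acceptability curve. The mixed models with participant and clinic random effects are described for effectiveness outcomes only. Multiple imputation is planned for missing data, which is a different matter from the precision of a ratio.

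Under Randomization and Interventions, "participants receive increasing rewards for consecutive negative UDS" in the high-intensity arm, up to 150 USD over 12 weeks, against at most 40 USD in the low-intensity arm. Responders then go to SMS maintenance. Non-responders are randomized to Matrix, or to Matrix plus contingency management.

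**The concern.** A CER is a ratio of two estimates. Its sampling uncertainty depends on the variance of each and on their covariance, and it becomes very large when the effect difference is small relative to its standard error. Moving one component at a time by one unit of spread captures neither feature.

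Followed as written, the plan would let Aim 2 report a point estimate and some shifted values, but not how sure the trial is that one strategy is better value than another. The results are meant for policy makers. The risk is greatest where effects are modest, because there the shifted values can look informative when the data cannot bound the ratio at all.

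**Working it through.** **Inputs from the documents (Sample size determination).** Base rates are 80-90% for substance use and 60-70% for viral suppression. The detectable difference is 20 points, with 80% power, 5% alpha, 20% attrition and 100 HIV-positive participants per group (80 after attrition). The total sample is 600. With 1:1 allocation assumed, that is 300 × 0.8 = 240 per arm.

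**Reproducing the plan's figure.** The documents give no precision for the CER, so the design difference is the only figure to reproduce. For 60% v 80% (two-sided 5%, no continuity correction), 82 per group are needed, or 82/0.8 ≈ 103 with attrition, close to the stated 100. Power with 80 per group is 79.4%. The 20-point figure holds and is used below.

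**Reading 1: SD of participants.** For a binary outcome SD = √(p(1−p)).
- 80% v 60%: √0.16 = 0.40 and √0.24 = 0.49. Then 0.20 − 0.40 = −0.20 and 0.20 − 0.49 = −0.29. The upper ends are 0.60 and 0.69.
- 90% v 70%: √0.09 = 0.30 and √0.21 = 0.46. Then 0.20 − 0.30 = −0.10 and 0.20 − 0.46 = −0.26.

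At the plan's base rates and difference the denominator changes sign, so the shifted range of the ratio has no interpretation.

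**Reading 2: standard error of the effect.** SE = √(0.24/240 + 0.16/240) = 0.041. The effect range is 0.16 to 0.24 and does not cross zero. One SE either side covers 68.3% for a single normal estimate.

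**The plan's own example: adding contingency management to Matrix in non-responders.** The section on modified eligibility says at least 50% of the sample must enter the adaptive phase. That is 300 of 600, or 150 per arm if allocation is equal, and 150 × 0.8 = 120 after attrition. Assume 80% v 70%:
- SE = √((0.16 + 0.21)/120) = 0.056, and z = 0.10/0.0555 = 1.80.
- The Fieller set is bounded only if ΔE² − 1.96² × SE² > 0. Here 0.0100 − 3.84 × 0.00308 = −0.0018, so the 95% set is unbounded whatever the costs.
- The one-SE shift gives 0.044 to 0.156, hence a ratio from 0.10/0.156 = 0.64 to 0.10/0.044 = 2.25 times the estimate. That looks finite.

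**Joint uncertainty, with assumed costs.** The documents give no cost difference or cost SD. Assume ΔC = 60 USD and participant cost SD = 60 USD, with ΔE = 0.20, so CER = 60/0.20 = 300 USD. SE(ΔC) = 60 × √(2/n), which is 5.48 at 240 per arm and 9.49 at 80.

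| Per arm | Effect shift, ±1 SE | Cost shift, ±1 SE | Fieller 95%, corr. −0.6 | corr. 0 | corr. +0.6 |
|---|---|---|---|---|---|
| 240 | 249-377 | 273-327 | 185-560 | 203-512 | 227-456 |
| 80 | 222-464 | 253-347 | 134-1169 | 157-997 | 193-813 |

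In simulation (400,000 draws, cost SD 40 or 60 USD, correlation −0.6 to +0.6), the two shifts taken together covered the true ratio in 55-78% of draws at ΔE = 0.20. At ΔE = 0.10 they covered 62-74% with 240 per arm and 49-56% with 80. The cost shift alone covered 11-42%.

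**Sign of the link.** A toy model with assumed urine-screen patterns gave a participant-level correlation of cost with response of about +0.6 to +0.7 from rewards alone. It gave −0.4 to −0.99 once an assumed 100-200 USD Matrix cost fell on non-responders.

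**The case against.** The plan calls these steps sensitivity analyses of assumptions about effect size and cost. It does not present them as a confidence interval, and one-way deterministic analysis is a legitimate, limited tool. This stands: the defect is an omission, and the 68% figure describes what the shift would be if used as an interval, not a claim the plan makes. That the shifts are one at a time is likewise an inference from two separate sentences, though nothing joint is described.

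A reader might infer three stronger things that the documents do not support.
- *That a participant-SD shift crosses zero for any binary outcome.* It does not: at 90% v 40% the effect is 0.50 and the larger SD is 0.49. Crossing holds at the plan's base rates and 20-point difference. Quality of life, also a cost-effectiveness outcome, is not binary.
- *That both readings of the SD fail in the same way.* The standard error is arguably the more natural reading, and at the planned effect it produces no sign change. Its faults are low coverage and neglect of the covariance.
- *That cost and effect rise together by design.* Rewards push that way, but response also moves participants to SMS and away from Matrix, with later costs counted. For viral load and quality of life, rewards are not tied directly to the outcome. The sign depends on unit costs that the documents do not give, so ignoring the link may make uncertainty look too wide or too narrow.

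It is also fair to say that net benefit with acceptability curves is one good option among several. An interval for the ratio, or for the two increments jointly, would fill the core gap.

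**Conclusion.** The point holds as an omission with an ambiguity. Aim 2 has no planned statement of sampling uncertainty for its ratios, the SD in the sensitivity analysis is undefined, and a cost-effect correlation created by the design is left out. If the SD is a standard error, each shift is about a 68% range for one component, and at an assumed 80% v 70% with 120 per arm it looks finite where the 95% set is unbounded. If it is a participant SD, the denominator becomes negative at the planned 20-point difference (−0.10 to −0.29).

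The dollar ranges and coverage figures rest on assumed cost differences, cost SDs and correlations, so only their pattern should be relied on. The 120-per-arm example assumes equal allocation, 50% non-response and a 10-point effect. None of this questions the sample size or the effectiveness analysis. The change should be made before the economic analysis is run.

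**What to change.** 1. **Cost each participant.** Apply unit costs to each person's recorded sessions and incentive payments. Activity-based costing is planned by arm, so state a rule for allocating shared delivery costs.
2. **Estimate incremental cost and effect jointly.** Use a bootstrap that keeps each participant's cost and outcome paired over the whole treatment path, accounts for clinic and arm, and is combined with the planned multiple imputation. Say how clinics are handled: resampling only within clinic and arm holds the 20 clinics fixed and leaves cells of about 600/20/2 = 15. A net-benefit regression with a clinic effect is an alternative.
3. **Report** 95% intervals for incremental cost, incremental effect and incremental net benefit over a stated willingness-to-pay range, with an acceptability curve.
4. **Keep the one-SD shifts as supplementary**, with the SD defined.

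The cost is analysis work and a change to the plan's wording, with the ethics approval that the protocol requires for amendments. Recruitment and treatment are untouched, and linked participant identifiers are already planned. The downsides are that a willingness-to-pay range and an allocation rule must be chosen and defended, and that the reported uncertainty may be wider than the present plan would show.
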